5.22 Outlier

An outlier value is defined as a value that lies outside the interval ($Q1 - 1.5 \cdot IQR$, $Q3 + 1.5 \cdot IQR$), where $Q1$ and $Q3$ are Quartiles 1 and 3, respectively, and IQR is the interquartile range, ie, $Q1 - Q3$ of the underlying distribution during the pre- or post-UX007 treatment period.

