5 DEFINITIONS

5.1 Pharmacokinetic Objectives

- Characterize the steady-state pharmacokinetics (PK) of UX007 and UX007 metabolites in subjects with LC-FAOD

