5.21 Exposure-adjusted Adverse Event Incidence Rate

The exposure-adjusted adverse event incidence rate is defined as the total number of occurrences of an AE summed across all subjects in the group divided by the total observation time for AEs for subjects in that group. The observation time for each subject is the duration from study day 1 (i.e., first dose of UX007) till the end of study period 1 or the date of clinical cutoff, whichever occurs earlier. The total observation time for AEs is the sum of observation times for all subjects in that group.

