8.5.4.1 Pre- and Post-UX007 Comparisons in MCE in Triheptanoin-Naïve Cohort

All MCE related endpoints (i.e., annualized event/duration rates of MCE overall and by event type) will be analyzed by comparing pre- and post-UX007 treatment period. The pre-UX007 treatment period for UX007/trihep naïve subjects corresponds to the retrospective MCE collection period, i.e., study period 3.

The 18 months pre-UX007 treatment period will be compared to the 18 months post-UX007 treatment period using the paired t-test. The Wilcoxon signed rank test will be performed as a nonparametric alternative to the paired t-test when the normality assumption is questionable. For subjects who had longer than 18 months of follow up on study as of the data cutoff date, MCEs that occurred between UX007 initiation and 18 months post UX007 initiation will be

included for calculating number of MCEs and total durations in days of MCEs will be calculated accordingly. For subjects who terminated the study prior to reaching 18 months on study, MCEs that occurred between UX007 initiation and the termination visit will be included for calculating number of MCEs and total durations in days of MCEs will be calculated accordingly. For historical annualized event rate and annualized duration rate observed during study period 3, the data collection period is 18 months (548 days) preceding the date of UX007 initiation. For subject's age less than 18 months at UX007 initiation, the data collection period will be between the birthdate and the date prior to UX007 initiation.

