8.5.4.2.2 Removing Outliers in Triheptanoin-naïve

Sensitivity analysis will be performed by removing identified outliers in pre- and post-UX007 treatment periods for:

- Annualized event rate of MCEs and MCE hospitalizations
- Annualized duration of event rate of MCEs and MCE hospitalizations

See definition of outlier in section 5.21.

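### SAP 5.22 prints the interquartile range with the wrong sign and, once that is corrected, still has no workable outlier rule when Q1 = Q3

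*SAP*

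**What the plan says.** SAP 5.22 holds the only definition of an outlier in either document. It begins "An outlier value is defined as a value that lies outside the interval", gives the limits Q1 - 1.5 x IQR and Q3 + 1.5 x IQR in round brackets, and adds that "IQR is the interquartile range, ie, $Q1 - Q3$ of the underlying distribution during the pre- or post-UX007 treatment period".

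In the body of the SAP the rule is used in 8.5.4.2.2, for the treatment-naive cohort: "Sensitivity analysis will be performed by removing identified outliers in pre- and post-UX007 treatment periods for" two pairs of endpoints. The first pair is "Annualized event rate of MCEs and MCE hospitalizations"; the second is the matching annualized durations. The summary of changes at the front of the SAP says that the purpose is to confirm that the main MCE finding is robust.

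Section 8.5.4.2.2 then directs the reader: "See definition of outlier in section 5.21". In the body, that number belongs to "5.21 Exposure-adjusted Adverse Event Incidence Rate", and Outlier is 5.22. The contents list still shows Outlier at 5.21. The body numbering of section 5 moved by one because its first heading is now "5.1 Pharmacokinetic Objectives".

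**The concern.** The definition is the operative rule for a planned analysis, and as printed it cannot be run: no value can lie inside an interval whose lower limit is above its upper limit. A programmer will almost certainly compute Q3 - Q1 instead.

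Correcting the sign does not finish the job. The trimmed variables are annualized event and duration rates over roughly 18 months, and these contain many exact zeros. If enough subjects have no event in a period, both quartiles are zero and the limits collapse to a point. Neither 5.22 nor 8.5.4.2.2 says what to do then. Someone would have to decide after seeing the data, in an analysis that exists to show that the result does not depend on a few subjects.

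**Working it through.** The plan gives no figure to reproduce here, so the check applies the rule itself.

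**1. Sign as printed.** Let D = Q3 - Q1 > 0, so the printed IQR is -D.
- Lower limit: Q1 - 1.5(-D) = Q1 + 1.5D.
- Upper limit: Q3 + 1.5(-D) = Q3 - 1.5D.
- Lower minus upper: (Q1 - Q3) + 3D = 2D > 0. The interval is empty.

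Invented example of 12 rates: 0, 0, 0.67, 0.67, 1.33, 1.33, 2, 2, 2.67, 3.33, 4, 12. Here Q1 = 0.67, Q3 = 3.00 and D = 2.33.
- As printed: lower 0.67 + 3.495 = 4.165, upper 3.00 - 3.495 = -0.495. All 12 of 12 values are flagged.
- Sign corrected: (-2.825, 6.495). One value (12) is flagged.

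**2. Sign corrected, Q1 = Q3.** Take 12 subjects, 10 with rate 0 and two with 0.67 and 2.0. Both quartiles are 0 and the interval is (0, 0).
- Open limits, as printed: 12 of 12 removed, zeros included.
- Closed limits: the two subjects with events are removed and a period with no events is left.

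The duration rates have the same zeros and fail in the same way.

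**3. How often this could arise.** The documents give no event-free proportion, so what follows rests on assumptions.

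The window is 548 days (SAP 8.5.4.1), that is 548/365.25 = 1.500 years. Counts are assumed gamma-Poisson with shape k, so a rate r gives mean count m = 1.5r and event-free probability p0 = (k/(k + m))^k. The rate at which p0 = 0.75:
- k = 1: m = 0.333, r = 0.222 per year.
- k = 0.5: m = 0.389, r = 0.259 per year.

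A rough anchor is the retrospective chart review in Protocol 5.2.3: 319/241 = 1.32 hospitalizations per year. That is a different cohort, with all-cause hospitalizations and the periods before and after treatment pooled. Starting from 1.32, the post-treatment rate would have to fall by 1 - 0.259/1.32 = 80% to 1 - 0.222/1.32 = 83% before p0 reached 75%.

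With n independent subjects, the third quartile is zero when more than 75% are event-free (16 or more of 20, 31 of 40, 46 of 60, with quartiles from the averaged empirical distribution). The binomial probability of this in the post period is:

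| Post rate per year | k | p0 | n = 20 | n = 40 | n = 60 |
|---|---|---|---|---|---|
| 0.66 (half of 1.32) | 1 | 0.502 | 0.6% | <0.1% | <0.1% |
| 0.66 | 0.5 | 0.579 | 3.4% | 0.8% | 0.2% |
| 0.41 (1.32 x 0.31) | 1 | 0.619 | 7.2% | 2.8% | 1.1% |
| 0.41 | 0.5 | 0.670 | 15.8% | 10.3% | 6.9% |

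The 0.41 row borrows the 69% fall that Protocol 5.2.3 reports for hospital days. Simulation under the same assumptions agreed: 0-4% of trials at 0.66 and about 1-17% at 0.41.

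A sparse extreme comes from Protocol 5.1: 25% of a newborn-screened group had a major decompensation within 2 years. At constant hazard, 0.75^(1.5/2) = 0.81 are event-free at 18 months, and IQR = 0 becomes more likely than not. That group is 16 patients, 3 of them with a disorder not among the diagnoses listed for this trial. Naive subjects here must have failed conventional therapy, so they should have more events.

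**The case against.** The strongest reply is that nothing will go wrong in practice. The text names the interquartile range and uses the usual 1.5 multiplier, so the meaning is plain; the printed expression may even have been meant as a range from Q1 to Q3. This stands as far as it goes. A reader might infer that the analysis will discard all the data, and the documents do not support that. The correction is still needed, because 5.22 is the only statement of the rule.

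It can also be said that IQR = 0 is improbable. At the assumed rates it is, and the anchor of 1.32 per year is too rough to lean on in either direction. That limits the weight of the gap but does not fill it.

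Three stronger readings should be set aside.
- **Values equal to a limit are undecided.** They are not. Round brackets, with the wording that an outlier lies outside the interval, make a tied value an outlier. Keeping such values would change the rule.
- **Trimming shrinks the treatment difference, so the rule is biased.** In simulation with closed limits, which the SAP does not print, about 7-12% of pairs were dropped and the mean paired difference shrank by 12-35%. Any correctly written rule that removes high values from skewed data does this. It is a caution for interpretation and does not measure this defect.
- **The handling of a flagged subject's other value undermines the comparison.** Section 8.5.4.1 says that "The 18 months pre-UX007 treatment period will be compared to the 18 months post-UX007 treatment period using the paired t-test", and a paired test loses the pair anyway. Section 8.5.4.2.2 does not call for a trimmed rerun of the negative binomial model.

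**Conclusion.** Wrong as written, minor. The sign error is certain and follows from algebra alone. The missing provision for Q1 = Q3 is also certain as a matter of text; how likely it is to matter depends on assumed rates, dispersion and a cohort size of 20 to 60. On those assumptions it is uncommon for MCE hospitalizations at a post-treatment rate of 0.66 per year, reaches about one trial in six in the least favorable case at 0.41, and would be expected only if events were much sparser than the anchor suggests. The cross-reference is a clerical slip.

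The effect is confined to the outlier-removal sensitivity analysis in the naive cohort. A reader might infer that the primary result is at risk. It is not: SAP 8.5.1 specifies descriptive statistics of the annualized MCE rate over study period 1, and the outlier rule plays no part in them.

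**What to change.** - In SAP 5.22, write IQR = Q3 - Q1.
- In SAP 8.5.4.2.2, state that an endpoint is not trimmed when IQR = 0 in either period, and that the output will say so.
- In the same section, require the number of subjects and the number of events removed to be reported for each period.
- Editorial: confirm in words that the open interval is intended, and change the cross-reference from 5.21 to 5.22.

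The cost is a few lines of SAP text. The one drawback is that a sparse endpoint may have no trimmed result.

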6 ANALYSIS POPULATIONS

6.1 Full Analysis Set (FAS)

The full analysis set (FAS) will consist of all subjects enrolled and had at least one post-baseline efficacy assessment. The full analysis set will be used for efficacy analyses.

6.2 Safety Analysis Set

The safety analysis set consists of all subjects who were enrolled and treated with at least 1 dose of UX007 while on CL202.

6.3 Full Analysis Set-SF-10

The full analysis set – SF-10 is the subset of subjects in the full analysis set whose age at enrollment was ≥ 6 to <18 years old and who had at least one SF-10 test performed while on study CL202.

6.4 Full Analysis Set-SF-12

The primary analysis set – SF-12 is the subset of subjects in the full analysis set whose age at enrollment was ≥ 18 years old and who had at least one SF-12 test performed while on study CL202.

6.5 PK Sub-study Set

The PK sub-study set consists of subjects who participated in PK assessments at selected sites.

7 DATA SCREENING AND ACCEPTANCE

7.1 General Principles

Data will be reviewed periodically. Any questionable data will be reported to the clinical data manager promptly for query and resolution.

7.2 Handling of Missing and Incomplete Data

Missing clinical outcome data can occur for multiple reasons, including missed subject visits and scales or measures with missing item scores. Missing and incomplete data will be identified through the data quality review plan for this study. Missing and incomplete data will be identified for investigation, and possible resolution be done by Data Management prior to the final study database lock or interim snapshot.

Unless specified otherwise, only the observed data (not imputed data) will be presented in listings.

7.2.1 Missing Medical History Related Dates

To impute a missing date related to medical history, for example, diagnosis date, the following rules will be applied:

- If only day is missing, impute 1.
- If month is missing, impute January 1st.
- If year is missing, then no imputation will be done; the date will be missing.

If the imputed date is earlier than the birth date, then the birth date will be used.

7.2.2 Missing Birth Dates

To impute missing birth date, the following rules will be applied:

- If day is missing, impute 15.
- If month is missing, impute June.
- If year is missing, then no imputation will be done; the date will be missing.

If the imputed date is later than any study visit date/observed adverse event start date/observed concomitant medication start date, then earliest available visit date/adverse event start date/ concomitant medication start date will be used without changing observed information.

7.2.3 Missing Date Imputation for Adverse Events and Concomitant Medications

The following conventions will be used to impute missing portions of dates for adverse events and concomitant medications. Note that the imputed values outlined here may not always provide the most conservative date.

Missing Start Dates

- If the day is unknown, then:
 - If the month and year match the first dose of investigational product start date month and year in this study, then impute the day of the first dose date.
 - Otherwise, assign the first day of the month.
- If the month is unknown, then:
 - If the year matches the year of the first dose of investigational product date in this study, then impute the month and day of the first dose date in this study.
 - Otherwise, assign 'January'
- If the year is unknown, then the date will not be imputed and will be assigned a missing value.

If the imputed date is earlier than birth date, then birth date will be used. If the imputed start date is later than the end date, then the start date will be set as the same date as the end date.

Missing Stop Dates (not applicable to ongoing)

- If the day is unknown, then assign the last day of the month.
- If the month is unknown, then assign 'December.'
- If the year is unknown, then the date will not be imputed and will be assigned a missing value, and the event will be considered ongoing. If the AE has been recorded as resolved/recovered, all efforts should be made to obtain the date from the Investigator.
- If the resulting end date is after the date of study completion / discontinuation/ data cutoff, set the imputed end date as close to the date of study completion / discontinuation/ data cutoff as possible without overwritten existing information.

If the year is missing for the start date and the stop date (observed or imputed) is on or after the first dose or event is ongoing, the start date will be imputed as the first dose date.

7.2.4 Missing Data for Efficacy Endpoints

For efficacy endpoints based on the duration of study period, the date of the study exit needs to be available. In case it is missing, the study period will end at the date of last assessment.

When a change from baseline is assessed, missing data will not be imputed and only subjects with a baseline and at least one post-baseline measurement will be included in the analysis.

7.2.5 Missing Causal Relationship to Investigational Product for Adverse Event

If the causal relationship to the investigational product is missing for an AE that started on or after the date of the first dose of UX007, a causality of “definitely related” will be assigned. The imputed values for causal relationship to investigational product will be used for the incidence summary, but be reported as collected and shown as missing in the data listings.

7.2.6 Visit Window

In general, all summary tables by visit include all scheduled assessments per schedule of assessments. Assessments scheduled at a planned study visit but are collected during an unscheduled visit or early termination visit will be mapped into the closest study visit based on the study day of the unscheduled visit or early termination visit, and the schedule of assessment in the protocol.

The mapped unscheduled visit will not be used unless the scheduled visit is missing. If a subject early terminated the study, the early termination visit will be mapped to the closest scheduled visit.

In case of multiple unscheduled assessments fall into the same scheduled visit, the earlier one is taken.

7.3 Testing/Validation Plan

Data will be reviewed by cross functional team periodically and issues will be addressed by clinical data management.

7.4 Software

SAS[®] software version 9.4 or higher will be used to perform statistical analyses unless otherwise specified.

8 STATISTICAL METHODS OF ANALYSES

8.1 General Principles

This statistical analyses are mostly descriptive analyses with statistical tests performed for select. All statistical tests will be two-sided and tested at statistical significant level of 0.05. The statistical analyses will be reported using summary tables, figures, and data listings. Continuous variables will be summarized by number of subjects and mean, standard deviation (SD), median, minimum, and maximum values. Categorical variables will be summarized by number and percentage of subjects. All raw data obtained from the CRFs will be included in data listings

8.1.1 Repeated Measure Model: General Estimating Equations

When the sample size and number of observations are allowed, change from baseline endpoints over time will be analyzed using a generalized estimation equation (GEE) model that includes time as the categorical variable and adjusted for the baseline measurement. The covariance structure that will be used for the GEE model is compound symmetry which specifies constant variance for the assessments and constant covariance between the assessments over time. In general, the p-value will be presented for testing the statistical significance of the change from the baseline to assessments at Months 6, 12, 24, 60, 72, and 84, if applicable, respectively. For an analysis of change from baseline to assessment at a particular month, only measurements up to that month will be included in the model. For the analysis of change from baseline to assessments at Month 84, all measurements collected up to and including Month 84 will be included in the model.

If the number of observations are insufficient for analyses using a GEE model, a descriptive summary will be provided, and analyses using observations at a single time point, such as paired t-test or other nonparametric methodologies, may be considered.

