3.4 Blinding and Randomization Methods

Since this is a single-arm open label study, hence randomization and blinding are not applicable.

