8.5.4.3 Analyses of Non-MCE Endpoints in Triheptanoin-naïve Cohort

When the sample size and number of observations are allowed, statistical tests will be performed on the following non-MCE endpoints to assess the statistical significance of change from the baseline to assessments at Months 6, 12, 24, 60, 72, and 84 if applicable, respectively. Two-sided 95% confidence interval and p-value will be presented at these visits.

- Echo variables: EF, ventricle size, and SF: the paired t-test will be used to assess the statistical significance of change from baseline variables. The Wilcoxon signed rank test will be performed if the normality assumption is questionable.
- Clinical biomarkers: the paired t-test will be used to assess the statistical significance of change from baseline variables. The Wilcoxon signed rank test will be performed if the normality assumption is questionable.
- SF-10 PHS and PSS: the GEE model as described in Section 8.1.1 will be used to analyze change from baseline scores.
- SF-12v2 PCS & MCS: the GEE model as described in Section 8.1.1 will be used to analyze change from baseline scores.

Statistical testing of the above endpoints will only be performed at the final analysis when the sample size permits. Summary statistics will be provided by visit at a snapshot analysis due to the anticipated limited number of subjects and number of observations at the time of a snapshot. Two-sided 95% confidence intervals will be presented for change from baseline values at all visits.

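### The baseline-adjusted GEE for SF-10 and SF-12 change in the single-arm naïve cohort leaves the sampling error of the baseline mean out of its standard error

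*SAP*

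**What the plan says.** SAP 8.1.1 takes change from baseline as the outcome, which "will be analyzed using a generalized estimation equation (GEE) model that includes time as the categorical variable and adjusted for the baseline measurement". On the working correlation it states that "The covariance structure that will be used for the GEE model is compound symmetry". The hypothesis concerns mean change in the cohort: "the p-value will be presented for testing the statistical significance of the change from the baseline to assessments at Months 6, 12, 24, 60, 72," with Month 84 closing the list.

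SAP 8.5.4.3 applies the model to two instruments in the naïve cohort: "SF-10 PHS and PSS: the GEE model as described in Section 8.1.1 will be used to analyze change from baseline scores" and "SF-12v2 PCS & MCS: the GEE model as described in Section 8.1.1 will be used to analyze change from baseline scores". It asks for a two-sided 95% confidence interval and a p-value at the tested months. SAP 8.1 sets the level: "All statistical tests will be two-sided and tested at statistical significant level of 0.05". SAP 3.4 confirms that there is no comparator: "Since this is a single-arm open label study, hence randomization and blinding are not applicable".

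Two things are not stated: the baseline value at which the adjusted visit mean is read, and any step that carries the sampling error of the baseline mean into its standard error. For ECHO variables and biomarkers, SAP 8.5.4.3 uses a paired t-test on change (or the Wilcoxon signed rank test), with no baseline covariate.

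**The concern.** Adjusting for baseline is sound when two arms share a baseline distribution, because the uncertainty in the baseline mean then largely cancels from the difference. Here the estimand is a one-sample mean change and nothing cancels. With complete data, the visit mean read at the sample mean baseline equals the raw mean change, so the covariate leaves the estimate alone and shrinks only its error.

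The p-value then answers a different question: whether mean change is zero with the baseline mean fixed at the value that happened to be observed. A baseline mean that is low or high by chance makes rejection more likely than the nominal level allows. At stake are the p-values and intervals for the SAP's only model-based tests of functional change, in an uncontrolled open-label study.

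**Working it through.** **Inputs.** Two-sided level 0.05 (SAP 8.1). One arm (SAP 3.4). Change as outcome, categorical time, baseline covariate, compound symmetry (SAP 8.1.1). Reference-population SD of 10 (SAP 5.19), which sets the scale only and cancels out of the error rate. The documents give neither the baseline-to-visit correlation r nor the number of naïve subjects with SF-10 or SF-12 data, so both are assumed. There is no power or precision figure to reproduce; the only stated target is the 5% level.

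**Closed form.** Let D be the change at a visit, B the baseline, and b the slope of D on B.

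1. True variance of the mean change: Var(D)/n = Var(D | B)/n + b²·Var(B)/n.
2. The baseline-adjusted model uses only the first term.
3. With equal SDs s, Var(D) = 2s²(1−r), Var(D | B) = s²(1−r²) and b = r−1. Check: s²(1−r²) + s²(1−r)² = 2s²(1−r).
4. SE factor = sqrt[(1−r²) / (2(1−r))] = sqrt((1+r)/2). It does not contain n.
5. Actual type I error = 2·[1 − Φ(1.96 × factor)].

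| assumed r | SE factor | type I error | coverage of the 95% CI |
|---|---|---|---|
| 0.3 | 0.806 | 11.4% | 88.6% |
| 0.5 | 0.866 | 9.0% | 91.0% |
| 0.8 | 0.949 | 6.3% | 93.7% |
| 0.9 | 0.975 | 5.6% | 94.4% |

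With unequal SDs the size changes. For a follow-up to baseline SD ratio of 1.25 and r = 0.8, the slope of follow-up on baseline is 1.25 × 0.8 = 1, so b = 0 and the error is exactly 5%. For a ratio of 0.8 and r = 0.7 it is 12.1%. The omitted term is a square, so it never makes the SE too large.

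On the score scale, with n = 40, SD 10 and r = 0.5 (all assumed), the correct 95% half-width is 1.96 × sqrt(2 × 100 × 0.5 / 40) = 3.1 points. The adjusted model gives 3.1 × 0.866 = 2.7.

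**Simulation.** Normal scores, three post-baseline visits, equal correlation r = 0.5, no true change, complete data, test at the last visit. There were 20,000 replicates per cell (8,000 at n = 400). The sandwich SE used matched a fitted exchangeable GEE on a test data set.

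| n | adjusted GEE, robust z | adjusted GEE, df correction and t | GEE on change without covariate, robust z | paired t-test |
|---|---|---|---|---|
| 10 | 15.3% | 7.1% | 9.5% | 4.9% |
| 20 | 12.1% | 8.3% | 7.1% | 5.0% |
| 40 | 10.5% | 8.6% | 6.1% | 5.0% |
| 100 | 9.6% | 8.8% | 5.5% | 5.1% |
| 400 | 9.2% | 9.1% | 5.4% | 5.3% |

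The fourth column shows that part of the small-n excess in the second column is the ordinary sandwich problem, which is separate. The third column isolates the present point: the corrected test moves towards 9.0% as n grows, not towards 5%.

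**Missing visits.** A further simulation (r = 0.5, no change, 600 replicates) let the chance of reaching the last visit depend on baseline. Deleting the covariate from the change model biased the mean change by about −0.6 to −0.7 points. Treating baseline as the first time level was close to unbiased. It rejected in 8.7% (n = 20) and 7.7% (n = 40) of data sets, against 13.0% and 10.2% for the planned model. The Monte Carlo standard error near 10% is sqrt(0.1 × 0.9 / 600) = 1.2 points.

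**The case against.** The strongest reply is about reach, and it stands. SAP 4.3 lists SF-10 and SF-12 as exploratory. SAP 8.5.4.3 tests them only in the naïve cohort, at the final analysis, if sample size permits. SAP 8.1.1 falls back on description, and possibly a paired t-test, when data are sparse. The primary MCE analysis is descriptive, and the ECHO tests do not use this model. SAP 8.5 and 8.5.3.1 also place raw change summaries beside the GEE result, so a careful reader could rebuild the correct interval from n, mean and SD. That softens the harm but does not make the GEE p-value right.

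The size also depends on an unknown r, and at 0.9 it is slight.

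Several stronger readings are tempting but unsupported:

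- A reader might infer that the test rejects whenever the baseline mean is off by chance. It only rejects more often than 5%, at the rates shown.
- A reader might suppose that uncentred visit coefficients would be tested, meaning change at a score of 0. Nothing in the SAP says so; it speaks of change at each month.
- A reader might expect the error to be worst at Months 60 to 84. That requires the correlation with baseline to fall over time, on which the documents give no figure.
- A reader might link this to regression to the mean from enrolling subjects with unmet need. That affects any single-arm before-and-after test, and the fix does not address it.

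**Conclusion.** The point holds, at minor severity. With the adjusted mean read at the sample mean baseline, the SF-10 and SF-12v2 tests of change in the naïve cohort have standard errors that are too small whenever change is related to baseline, and the shortfall persists at every sample size. For assumed r from 0.3 to 0.9 with equal SDs, the large-sample type I error runs from 11.4% down to 5.6%; it is 5% when follow-up has slope 1 on baseline. With complete data the point estimate is unaffected. A reader might infer that the study's main efficacy findings are compromised, but no primary or secondary endpoint is analysed with this model.

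**What to change.** In SAP 8.1.1, for these one-sample tests, take the observed scores as the response, with baseline as the first level of the categorical time factor and no baseline covariate. Test the contrast Month m minus baseline and report it with its 95% confidence interval. Refer to this model in SAP 8.5.4.3 for SF-10 PHS/PSS and SF-12v2 PCS/MCS.

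Do not simply strike the covariate from the change-score model. When missing visits depend on baseline, as they may over up to 7 years, that biases the estimate. A small-sample correction to the sandwich variance is a separate matter; the rejection rates of 8.7% and 7.7% under the new model show that it would still be useful in a small cohort.

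The cost is a few lines of text and one changed model statement, with no new data. Confidence intervals widen by 1/0.949 − 1 = about 5% at r = 0.8 and 1/0.806 − 1 = about 24% at r = 0.3, and p-values become less favourable.
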